6.3 Secondary Outcomes

The secondary endpoints will include the following:

- Positive Predictive Value (PPV), Negative Predictive Value (NPV), and Diagnostic Accuracy will be calculated for Cytuity™ as compared to surgical histology of the ovaries and fallopian tube for fallopian tube involvement.
- Sensitivity, specificity, PPV, NPV, and accuracy will be calculated for Cytuity™ as compared to surgical histology of the fallopian tube.
- Sensitivity, specificity, PPV, NPV, and accuracy will be calculated for Cytuity™ as compared to surgical histology of the ovaries for epithelial malignancies.*
- Sensitivity, specificity, PPV, NPV, and accuracy will be calculated for Cytuity™ as compared to surgical histology for fallopian tube involvement for subject level analysis.

*Epithelial cancers, which consist of high and low-grade serous carcinomas, endometrioid, clear cell and mucinous subtypes make up approximately 95% of all ovarian cancers.

6.4 Sample Size Determination

The Cytuity™ procedure will be performed on a maximum of 150 subjects.

Subjects will be recruited until Cytuity™ cytology results can be compared with the surgical histology in at least 32 subjects determined to have a malignant neoplasm or malignancy and 18 subjects determined by surgical histology of the excised tissues to be negative for malignancy.

As this analysis will be conducted on tube level, the sample size was converted to look at the number of tubes that would be required. Previous data suggest that when 1 fallopian tube is positive for malignancy, the subject's other tube is positive about 75% of the time, making a total correlation of 80% is a reasonable assumption. The following formula was used for the statistical conversion:

Statistical conversion from subjects to fallopian tubes yields a requirement of 56 tubes, or samples, positive for malignancy. This is because the left and right fallopian tube are treated as partially independent from one another in regard to the histology results (for example, if there is malignancy in the right tube, that does not mean that there is malignancy on the left).

Based on an assumed 20% prevalence rate of (subject-level) malignancy, a sample size of 140 subjects (280 tubes) in which both fallopian tubes are tested is statistically likely to produce the minimum 56 positive tubes required.

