5.3.4 Post-Operative Pathology

Per site standard procedures, excised tissue will be sent to site-specific pathology department/facility. The histological evaluation will include standard of care only (including micro-sectioning of the fallopian tubes); no different, unique or experimental methods will be used.

Transfer of each subject's surgical pathology (histology) report diagnostic data is a study requirement. All protected health information will be redacted by the site and the report will be labeled with the subject's study identification number. The redacted histology report will be provided to the sponsor. The redacted report will be reviewed by an independent study pathologist who will complete the study histology case report form. The study pathologist reviewing histology may contact the site's surgical pathology lab for clarification of the redacted report if warranted. If clarification is required, all communications between the site pathology lab and the study pathologist reviewing histology must be attached to the redacted report and included in the study data.

The study pathologist will use the redacted site pathology report to document the histology results of fallopian tube malignancy, ovarian malignancy, and other malignancy on a study case report form.

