6.5 Statistical Methods

This trial was designed with formal statistical hypotheses for both sensitivity and specificity. The sample size was determined based on a fallopian tube-level (each tube will be considered a data point), and assuming a high correlation of 75% between tubes in individual subjects. Previous data suggest that when 1 fallopian tube is positive for malignancy, the subject's other tube is positive about 75% of the time so making a total correlation of 75% is a reasonable assumption.

Since sensitivity is a function of diseased tubes only, while specificity is a function of non-diseased fallopian tubes, the statistical hypotheses for sensitivity and specificity are considered to be independent. Each hypothesis is framed as a 1-sided test with a type I error rate of 2.5%.

For sensitivity, the following hypothesis will be tested:

HNull: Sensitivity \leq 60% versus
HAlternative: Sensitivity $>$ 60%

For specificity, the following hypothesis will be tested:

HNull: Specificity \leq 70% versus
HAlternative: Specificity $>$ 70%

For the sample size calculation, the expected sensitivity of the Cytuity™ device is approximately 80% and the expected specificity is approximately 90%. Based on these parameters and requiring $>$ 80% power for both hypotheses above, 32 subjects positive for malignancy and 18 subjects negative for malignancy are required.¹⁴

Since this is a prospective study in which it is anticipated that the number of subjects testing negative will far exceed subjects testing positive, the sample size calculation is driven by the requirements for the sensitivity hypothesis. Conversion from subjects to fallopian tubes yields a requirement of 56 tubes positive for cancer.¹⁵ Based on an assumed 20% prevalence rate of (subject-level) malignancy, a sample size of 140 subjects (280 tubes) in which both fallopian tubes are tested is statistically likely to produce at least the 56 positive tubes required.

Because the primary analysis is based on fallopian tubes, the analysis must account for the subject-level correlation.¹⁶ A Logistic random-effects model will be used to calculate the point estimates and 95% (2-sided) confidence intervals for sensitivity and specificity.^{17,18} The adjustment proposed by Obuchowski will be performed for comparison.¹³

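### Recruitment stops on 32 subjects with any malignancy rather than on the 56 positive tubes the primary analysis needs, and the plan's own 20% prevalence makes either target unlikely by 150 subjects

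*Combined protocol and SAP*

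**What the plan says.** Section 6.4 sets the recruitment rule in subjects. Enrolment continues until there are "at least 32 subjects determined to have a malignant neoplasm or malignancy", each with a cytology result that can be set against histology. The rule also asks for 18 histology-negative subjects on the same terms. The section adds a ceiling: "The Cytuity™ procedure will be performed on a maximum of 150 subjects". The synopsis repeats both.

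The same section says the analysis is at tube level. Section 6.5 gives the corresponding target: "Conversion from subjects to fallopian tubes yields a requirement of 56 tubes positive for cancer". Sections 6.4 and 6.5 then state, "Based on an assumed 20% prevalence rate of (subject-level) malignancy", that 140 subjects with both tubes tested will probably yield those 56 tubes. Both sections report that when one tube is positive the other is positive about 75% of the time.

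Malignancy in the stopping rule is not restricted to the tube. The primary endpoint in section 6.2 is fallopian tube involvement, and under section 5.3.4 the study pathologist must "document the histology results of fallopian tube malignancy, ovarian malignancy, and other malignancy" on the case report form. Section 6.2 adds the favorable-discordance rule: a tube with negative histology is a true positive if the same-sided ovary and the tube's cytology are both positive.

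Section 5.2.4 restricts the endpoints to subjects with an adequate sample. Section 1.8 warns that access and adequacy may be lower with these investigators. The sample size text makes no allowance for such loss, and no passage says what follows if the cap is reached with the target unmet.

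**The concern.** There are two separate problems.

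The first is the unit. The 56-tube figure is called a requirement but is not part of the stopping rule. A subject with cancer confined to the ovary or elsewhere, or with one usable tube out of two, moves recruitment toward completion as much as a subject with two positive, evaluable tubes. The condition that cytology can be compared with histology screens out subjects with no usable sample, but it does not count tubes.

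The second is yield. Twenty per cent of 140 or of 150 is below 32, so the plan's own assumption does not lead to its own stopping count.

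At stake is the power of the sensitivity test, stated as above 80%. The trial could close as complete with fewer than 56 positive tubes, or reach the cap with neither target met. Neither can be repaired once recruitment has closed.

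**Working it through.** **Inputs.** From sections 6.4 and 6.5: null sensitivity 60%, expected sensitivity 80%, 1-sided 2.5%, power above 80%, prevalence 20%, 140 planned subjects, cap 150, other tube positive 75% of the time.

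**Reproducing the plan's figures.** With the variance taken at the alternative,

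n = (1.960 + 0.842)² × 0.8 × 0.2 / (0.8 − 0.6)² = 31.4, rounded up to 32 subjects.

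Tubes: 32 × (1 + 0.75) = 56. The conversion formula itself is not visible in the text available, so it is unclear whether 1.75 is a design effect or a mean number of positive tubes per malignant subject. Both give 56.

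Planned size: 140 × 0.20 × 2 = 56. This works only if every malignant subject is positive in both tubes, which conflicts with the 75%.

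**Expected yield.** Malignant subjects follow Binomial(N, 0.20). Positive tubes assume that every malignant subject has one positive tube and that the other is positive with probability 0.75, with no sample loss.

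| | N = 140 | N = 150 |
|---|---|---|
| Expected malignant subjects | 28 | 30 |
| P(at least 32 malignant) | 22.7% | 37.3% |
| Expected positive tubes (× 1.75) | 49.0 | 52.5 |
| P(at least 56 positive tubes) | 22% | 36% |
| P(at least 56) if all disease is bilateral | 53% | 69% |

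An expected count of 32 needs 32 / 0.20 = 160 subjects, or a prevalence of 32 / 150 = 21.3% at the cap.

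**Power by the plan's formula.** Taking 56 tubes as 32 subject-equivalents, m positive tubes give n = m / 1.75, and power = Φ(0.2 / √(0.16 / n) − 1.960).

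- 56 tubes: n = 32, power 80.7%.
- 52.5 tubes (expected at the cap): n = 30, power 78.2%.

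**If recruitment stops at 32 malignant subjects.** The proportion with tube involvement is not in the documents; 90%, 75% and 60% are an assumed range. Positive tubes = 32 × proportion × 1.75, before inadequate samples and without any favorable-discordance tubes.

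| Tube involvement (assumed) | Positive tubes | n | Power |
|---|---|---|---|
| 100% | 56 | 32 | 80.7% |
| 90% | 50.4 | 28.8 | 77% |
| 75% | 42 | 24 | 69% |
| 60% | 33.6 | 19.2 | 59% |

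**Inadequate samples.** With full involvement and 95%, 90% or 80% of tube samples adequate (assumed range), 56 tubes become 53.2, 50.4 or 44.8.

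**The case against.** The strongest case against is that the damage is modest on the plan's own assumptions. At the cap, with every malignant subject tube-positive and nothing lost, the expected shortfall costs about 2.5 points of power. Section 6.4 also calls 56 tubes a minimum and a requirement, so the subject count may be loose drafting and not an intention to ignore tubes. This stands as a limit on size. It does not remove the conflict between the two targets, or the fact that only the subject count is written as the stop.

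A reader might infer that malignant subjects without tube involvement contribute nothing to sensitivity. The documents do not support that: under section 6.2 a histology-negative tube enters the denominator as a true positive when the same-sided ovary and the cytology are positive. What remains is that such a tube's contribution depends on the test result, while the subject counts toward 32 regardless.

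A reader might also take 70 of 80 tubes (87.5%) from the earlier device study in section 1.3 as the expected usable proportion. Nine of the ten losses there were pre-existing occlusions. The present trial excludes known obstruction and tubal ligation, and among unblocked tubes adequacy was 70 of 71. Section 1.8 expects lower rates but gives no figure, so only an assumed range is defensible.

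Finally, if 1.75 is a design effect, 28 bilaterally positive subjects would supply 56 tubes, worth 32 independent observations, and 140 subjects would be coherent as a power statement. That still requires all disease to be bilateral, against the stated 75%, and still leaves 28 below the stopping count of 32.

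**Conclusion.** The concern holds. The stopping rule counts subjects with any malignancy while the primary analysis needs positive tubes, and at 20% prevalence neither 32 malignant subjects nor 56 positive tubes is expected by 150 procedures. The statement that 140 subjects will probably yield 56 tubes is wrong unless all disease is bilateral, and even then the chance is only 53%.

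The firm part of the cost is small: about 78% power at the expected cap yield against 80.7%. The larger losses, down to about 59%, depend on a tube-involvement rate that the documents do not give, and should be read as a range.

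The stronger reading, that the trial cannot reach its target, is not supported: 32 malignant subjects are still reached about 37% of the time at the cap. The result is also sensitive to prevalence. At 25% the expected count at 150 is 37.5 and the chance of 32 is 87%; at 15% they are 22.5 and 2%.

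**What to change.** In section 6.4 and the synopsis, state the stop as 56 tubes (or the reconciled number) that are positive on tube histology and have a paired evaluable cytology sample, or 150 procedures, whichever comes first. Describe this as a conservative count for the primary endpoint, since favorable-discordance tubes are left out of it.

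Have the tally kept by someone independent of the cytology classification. Favorable discordance depends on cytology. So does adequacy: the definition of an adequate sample accepts one with fewer than five clusters if it contains neoplastic or malignant cells. Without that separation, cytology results could influence when recruitment stops.

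In sections 6.4 and 6.5 and the synopsis, replace the claim about 140 subjects with the computed probability of reaching the target at 20% prevalence. Restate power at the expected tube count at 150, with a range for tube involvement and sample adequacy.

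The cost is protocol wording and a tube-level tally of data already collected. Recruitment becomes more likely to run to the existing cap, and the stated power becomes slightly less favourable. Because the cap stays, the change does not itself make 56 tubes likely (about 36% before sample loss); it makes the rule count the right unit and the stated power honest.

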	
compared to surgical histology of the ovaries and fallopian tube for fallopian tube involvement.
 
 2. Sensitivity, specificity, PPV, NPV, and accuracy will be calculated for Cytuity™ as compared to surgical histology of the fallopian tube. 3. Sensitivity, specificity, PPV, NPV, and accuracy will be calculated for Cytuity™ as compared to surgical histology of the ovaries. 4. Sensitivity, specificity, PPV, NPV, and accuracy will be calculated for Cytuity™ as compared to surgical histology for fallopian tube involvement for subject level analysis.

Statistical Methods for Primary Endpoint
	
The sensitivity of the Cytuity™ procedure is estimated to be 80%, while the specificity is estimated to be 90% for the primary endpoint of fallopian tube involvement.
 
Since sensitivity is a function of diseased fallopian tubes only, while specificity is a function of non-diseased fallopian tubes, the statistical hypotheses for sensitivity and specificity are considered to be independent. Each hypothesis is framed as a 1-sided test with a type I error rate of 2.5%.
 
For sensitivity, the following hypothesis will be tested:
 
H_{Null}: Sensitivity ≤ 60% versus H_{Alternative}: Sensitivity > 60%
 
For specificity, the following hypothesis will be tested:
 
H_{Null}: Specificity ≤ 70% versus H_{Alternative}: Specificity > 70%

Independent Core Labs
	
Pathology (surgical histology/pathology): Site specific redacted reports reviewed by independent study pathologist: [name] Pathologist Stanford University Medical Center
 
Cytology Core Lab (slide preparation) Calpath Medical Associates Campbell, CA
 
Pathologist #1 (cytology review): [name] Pathologist Santa Clara Valley Medical

	
Pathologist #2 (cytology review) [name] Pathologist Stanford University Medical Center
 
Pathologist #3 (cytology adjudication) [name] Pathologist University of California San Francisco

--	--------------------------------------------------------------------------------------------------------------------------------------------------------------------------------------------------------------------------------------------------

Table of Contents

Synopsis of the Clinical Investigation	2
Table of Contents.....	7
Definitions.....	9
1 Introduction.....	11
1.1 Current Treatment	11
1.2 Need for New Treatment.....	11

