1.3 Investigational Product

nVision Medical developed the MAKO 7 device to be used through the working channel of a hysteroscope for cell collection from the fallopian tube. nVision Medical was acquired by Boston Scientific Corporation in 2018 and the MAKO 7 is now called Cytuity™. The MAKO 7 and Cytuity devices are equivalent. The MAKO 7 / Cytuity™ device is FDA cleared as a hysteroscope accessory, placed through the working channel of a hysteroscope to obtain samples from the fallopian tube for cytological evaluation.

In a previous study, undertaken and submitted in support of FDA clearance, the MAKO 7/ Cytuity™ device was evaluated in forty (40) subjects (80 fallopian tubes) who were already scheduled to undergo a laparoscopic tubal ligation. Study endpoints included 1) ability of the device to navigate the fallopian tube, 2) ability of the device to collect a sample adequate for cytological evaluation, and 3) adverse events. Access was achieved in 71/71 (100%) of unblocked fallopian tubes and 71/80 (89%) of all tubes attempted. The nine (9) tubes that were not accessed were determined to have pre-existing tubal occlusion, as determined by methylene blue dye injection. The study pathologist determined that 70/71 (99%) of the samples were adequate for cytological evaluation. There were no adverse events reported.

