1.8 Required Training and Experience Needed to Use the Device

As cleared by the FDA, the Cytuity™ device requires that the device is “...to be used only by physicians who are knowledgeable hysteroscopists.”

Since this study requires access to an enriched patient population, i.e. patients who have malignancies, investigators may include gynecologic oncologists rather than the target user, gynecologists who are skilled at hysteroscopy. As a result, training not typically required of the target user will be provided for all investigators. Lower Cytuity™ device access rates and lower sample adequacy rates may be expected with this investigator population.

Prior to the start of the study, the investigator and clinical study staff will undergo training on the use of Cytuity™ device, the clinical study protocol, and study

procedures and requirements. Sponsor personnel (or designees) will conduct the training.

Clinical research staff will be supplied with the clinical protocol, device instructions for use, case report forms, and other supporting materials as needed.

Training of study personnel will be documented on the appropriate training record and maintained in the site study file and in the sponsor's trial master file.

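### The 140-subject figure assumes every tube gives an adequate sample; over the protocol's own 87.5% to 98.6% range it falls short of 56 expected positive tubes, and the 150-subject cap falls short below 93.3%

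*Combined protocol and SAP*

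**What the plan says.** Section 6.5 asks for power above 80% on each hypothesis and concludes that, at "80% power for both hypotheses above, 32 subjects positive for malignancy and 18 subjects negative for malignancy are required". The sensitivity test is against a null of 60% with 80% expected, one-sided at 2.5%. The 32 subjects become a requirement of 56 positive tubes. Section 6.4, repeated in 6.5 and the synopsis, then states that at an assumed 20% prevalence "a sample size of 140 subjects (280 tubes) in which both fallopian tubes are tested is statistically likely to produce the minimum" of 56. The procedure is limited to 150 subjects.

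Four other places bear on how many tubes will be evaluable:

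- Section 1.3 reports access in "71/80 (89%) of all tubes attempted" in the earlier study, and that "70/71 (99%) of the samples were adequate for cytological evaluation".
- Section 1.8 says that lower access rates and "lower sample adequacy rates may be expected with this investigator population".
- Section 5.2.4 evaluates primary and secondary endpoints in the modified intent-to-treat population, which requires an adequate sample.
- Section 6.5.1 leaves the treatment of missing and invalid data to the final report.

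**The concern.** The sample size counts tubes attempted, while the analysis can use only tubes with an adequate sample. The protocol reports losses in its earlier study, warns that they may be greater here, and analyses what remains, but the sample size contains no allowance for them. The 10 subjects between 140 and the cap are not described as an allowance. Read that way, they would cover 10/150 = 6.7% of procedures, against a 12.5% loss per attempted tube in the earlier study.

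At stake is whether the stated number of diseased tubes, and the power claimed from it, will be reached for the sensitivity hypothesis, which section 6.5 says drives the size.

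**Working it through.** **Inputs.** One-sided alpha 0.025, power above 80%, sensitivity 80% against 60%, specificity 90% against 70%, between-tube correlation 0.75 (all section 6.5); prevalence 20%, 140 subjects, cap 150 (section 6.4); access 71/80 and adequacy 70/71 (section 1.3).

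**Reproducing the plan.** With n = (1.960 + 0.842)² × p₁(1 − p₁)/(p₁ − p₀)²:

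- sensitivity: 7.849 × 0.16/0.04 = 31.4, so 32;
- specificity: 7.849 × 0.09/0.04 = 17.7, so 18.

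Tubes: 32 × (1 + 0.75) = 56. Total: 56/0.20 = 280 tubes, or 140 subjects. All the stated figures reproduce, with an evaluable fraction of exactly 1.00.

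**Evaluable fraction e in the protocol's data.** Per attempted tube, (71/80) × (70/71) = 70/80 = 87.5%. Per unblocked tube, 70/71 = 98.6%. Section 1.8 gives no figure, so 80% below is my assumption.

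**Expected positive tubes.** These keep the plan's step of taking 20% of tubes: 2 × N × e × 0.20.

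| e | 140 subjects: evaluable / positive | 150 subjects: evaluable / positive |
|---|---|---|
| 100% (plan) | 280 / 56 | 300 / 60 |
| 98.6% | 276.1 / 55.2 | 295.8 / 59.2 |
| 87.5% | 245 / 49 | 262.5 / 52.5 |
| 80% (assumed) | 224 / 44.8 | 240 / 48 |

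Break-even at the cap is 280/300 = 93.3%. At 87.5%, 280 evaluable tubes need 140/0.875 = 160 subjects; at 98.6% they need 142.

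**Chance of at least 56 positive tubes** (binomial, tubes treated as independent). With every tube evaluable, 140 subjects give 52%, because the expectation equals the requirement. At 87.5% the chance is 15% with 140 subjects and 32% at the cap. It is 36% at the cap if both tubes are positive in every malignant subject.

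**Power, plan's formula.** Power = Φ(√n_eff × 0.20/0.40 − 1.960). At 56 tubes n_eff = 56/1.75 = 32, giving 80.7%. With losses, n_eff depends on how they fall. The bounds below take D = 0.20N malignant subjects with both tubes positive, as 20% of tubes implies.

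- Losses in the same women: n_eff = T/1.75, where T = 2De.
- Losses independent between tubes: n_eff = T²/[3.5De² + 2De(1 − e)]. A remaining pair has variance weight 2 + 2 × 0.75 = 3.5 and a single tube has weight 1.

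| Subjects, e | T | n_eff: same women / independent | Power |
|---|---|---|---|
| 140, 98.6% | 55.2 | 31.5 / 31.7 | 80.2% / 80.4% |
| 140, 87.5% | 49 | 28.0 / 29.6 | 75.4% / 77.6% |
| 150, 98.6% | 59.2 | 33.8 / 34.0 | 82.8% / 83.0% |
| 150, 87.5% | 52.5 | 30.0 / 31.7 | 78.2% / 80.4% |
| 150, 80% (assumed) | 48 | 27.4 / 30.0 | 74.5% / 78.2% |

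**The case against.** The strongest reply is that 87.5% may not carry over. Nine of the ten tubes lost in the earlier study had pre-existing occlusion, and every unblocked tube was accessed. This trial excludes known obstruction and tubal ligation (section 5.2.2), and a ligation found at hysteroscopy makes the subject a screen failure (section 5.2.4). This stands in part: if all occlusion were screened out, 98.6% would apply and the cap would suffice. But only known obstruction is excluded and the schedule of assessments has no patency test, so undetected occlusion can recur. Even at 98.6%, 140 subjects are expected to give slightly fewer than 56 positive tubes.

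A second reply is that recruitment continues until 32 malignant and 18 negative subjects have comparable results, so 140 is only a projection. That is a fair reading of section 6.4, but the 150 maximum still ends recruitment.

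A third is that the effect on power is small. That stands: if losses are independent between tubes, the cap at 87.5% still gives 80.4%.

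A reader might infer three stronger things, none of which the documents support:

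- That the cap cannot deliver 56 positive tubes. It suffices in expectation above 93.3% evaluable, and at 87.5% the chance is still about one in three.
- That the protocol predicts worse than 70/80. Section 1.8 says only that lower rates may be expected than with the target user, without a figure.
- That 140 women must each have both tubes evaluable. The requirement is 56 positive tubes, and a woman with one adequate sample still contributes.

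**Conclusion.** The stated size rests on complete evaluability, which the protocol's own data contradict. With 140 subjects the expected number of positive tubes is below 56 at both ends of the documented range: marginally at 98.6%, and by 7 tubes at 87.5%. The cap is not expected to deliver 56 if fewer than 93.3% of tubes are evaluable; at 87.5% it falls 3.5 tubes short. Because the design starts only 0.7 points above its 80% power target, modest losses can take it below.

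These figures rest on the plan's own formula, a correlation of 0.75, and its step of applying the 20% prevalence to tubes. That prevalence is labelled subject-level. Whether it may be applied to tubes is a separate question, and this point does not depend on the answer.

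**What to change.** Restate sections 6.4 and 6.5 and the synopsis in evaluable tubes. Give:

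- the assumed access and adequacy rates and their source, including how far the eligibility criteria are expected to remove occluded tubes;
- the expected evaluable and evaluable-positive tubes at 140 subjects and at the 150 cap;
- the resulting power over 87.5% to 98.6%, stating whether losses are assumed to fall on the same women or independently.

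Replace the claim that 140 subjects are likely to produce 56 positive tubes with those expected counts.

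The cost is protocol wording and a slightly less favourable stated size and power. The correction itself requires no change in enrolment. If the sponsor wants 280 evaluable tubes at 87.5%, the figure to weigh is 160 subjects, which is above the present cap.

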Study Design	The study is a prospective, multi-center, non-randomized study. Study subjects will be recruited from a population of women who are already scheduled to undergo salpingo-oophorectomy or salpingectomy. The study protocol requires hysteroscopic sampling of the fallopian tube with the Cytuity™ device at the time of scheduled surgery. Cytology results from the cells collected using the Cytuity™ will be independently evaluated at a core lab and compared to the respective clinical site’s histological evaluation of the excised tissue. The histology results will not be shared with the core lab to avoid bias. Additionally, cytology results will not be shared with the study’s subjects or study investigator as no medical decisions will be made based on Cytuity™ results. Any baseline testing, surgical histology evaluations, and all other clinical care will be in accordance with each participating institution’s standard

	of care for patients undergoing salpingo-oophorectomy or salpingectomy.
Risk Status	The Cytuity™ device will be used in subjects at the time of scheduled surgery. Because the tissue that the Cytuity™ device contacts will subsequently be removed and because the device has been cleared by the FDA for use in obtaining samples from the fallopian tube for cytological evaluation, this study is proposed as a Non-Significant Risk (NSR) study.
Investigational Sites	Up to 15 clinical sites may participate in this study
Number of Participants	
The Cytuity™ procedure will be performed on a maximum of 150 subjects.
 
Subjects will be recruited until Cytuity™ cytology results can be compared with the surgical histology in at least 32 subjects determined to have a malignant neoplasm or malignancy and 18 subjects determined by surgical histology of the excised tissues to be negative for malignancy.
 
Statistical conversion from subjects to fallopian tubes yields a requirement of 56 tubes, or samples, positive for malignancy. This is because the left and right fallopian tubes are treated as partially independent from one another in regard to the histology results (for example, if there is malignancy in the right tube, that does not mean that there is malignancy on the left).
 
Based on an assumed 20% prevalence rate of (subject-level) malignancy, a sample size of 140 subjects (280 tubes) in which both fallopian tubes are tested is statistically likely to produce the minimum 56 positive tubes required.

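### If the assumed 20% prevalence is subject-level, as labelled, 140 subjects are not likely to yield 56 positive tubes, and the 150-subject cap gives an expected 30 malignant subjects against the 32 required

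*Combined protocol and SAP*

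**What the plan says.** The sample size text is in the synopsis (Number of Participants) and in Sections 6.4 and 6.5 of the combined protocol and SAP.

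- **Subjects required.** Section 6.5: "32 subjects positive for malignancy and 18 subjects negative for malignancy are required", for more than 80% power on each hypothesis. The sensitivity test is 80% expected against a null of 60%, one-sided at 2.5%.
- **Recruitment rule.** In Section 6.4 and the synopsis, enrolment continues until cytology can be set against histology "in at least 32 subjects determined to have a malignant neoplasm or malignancy", and in 18 negative subjects.
- **Cap.** "The Cytuity™ procedure will be performed on a maximum of 150 subjects".
- **Tubes required.** 32 subjects are converted to 56 positive tubes. Section 6.4 says that when one tube is positive the other is "positive about 75% of the time, making a total correlation of 80% is a reasonable assumption". Section 6.5 starts from the same 75% observation and states a correlation of 75%.
- **Prevalence.** All three places open the yield statement in the same way: "Based on an assumed 20% prevalence rate of (subject-level) malignancy, a sample size of 140 subjects (280 tubes".
- **Yield.** The conclusion in Section 6.4 and the synopsis is that "140 subjects (280 tubes) in which both fallopian tubes are tested is statistically likely to produce the minimum 56 positive tubes". Section 6.5 puts it that this sample "is statistically likely to produce at least the 56 positive tubes required".

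**The concern.** The prevalence is labelled subject-level each time it appears. A subject-level rate of 20% applied to 140 women gives 28 malignant subjects. Twenty-eight subjects can supply 56 positive tubes only if both tubes are positive in every one of them, yet the same sections say that the second tube is positive about 75% of the time. The subject target of 32 also lies above the expected count at the cap.

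Section 6.5 says that the sensitivity hypothesis drives the sample size. This step therefore justifies enrolment for one of the two primary hypotheses, and a reader would take from it that the planned sample will probably deliver the required positives.

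**Working it through.** **Reproducing the plan's figures**

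1. *Subjects.* With the variance taken at the alternative, n = (1.960 + 0.842)² × p₁(1 − p₁)/(p₁ − p₀)². Sensitivity (0.60 against 0.80) gives 31.4, rounded up to 32. Specificity (0.70 against 0.90) gives 17.7, rounded up to 18. Both match.
2. *Tubes.* The conversion formula did not survive in the text available to me, so its form is inferred. With a factor 1 + ρ, 32 × 1.75 = 56.0, which matches, and 32 × 1.80 = 57.6, which does not. Only the Section 6.5 correlation gives 56.
3. *Enrolment.* 56/(2 × 0.20) = 140, an exact match. This step multiplies all 280 tubes by 20%.

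**Malignant subjects at 20% subject-level**

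- 140 × 0.20 = 28. Binomial P(at least 32) = 0.227.
- 150 × 0.20 = 30. Binomial P(at least 32) = 0.373, so the chance of reaching the cap first is 1 − 0.373 = 0.627.

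**Positive tubes at 20% subject-level**

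Let q be the proportion of affected subjects with both tubes positive. I assume that every malignant subject has at least one involved tube and that all tubes are sampled and adequate. The expected number of positive tubes is N × 0.20 × (1 + q). The probabilities come from exact convolution over subjects.

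The 75% can be read in two ways. It may be the share of affected subjects who are bilateral (q = 0.75). It may instead be the chance that the other tube is positive given that a particular tube is; then q/(1 + q/2 − 1/2) is 0.75 and q = 0.75/1.25 = 0.60. The 80% in Section 6.4 can be read in the same two ways.

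| Reading | q | Tubes at 140 | P(≥56) at 140 | Tubes at 150 | P(≥56) at 150 |
|---|---|---|---|---|---|
| 75%, given a particular tube | 0.60 | 44.8 | 0.094 | 48.0 | 0.182 |
| 80%, given a particular tube | 0.667 | 46.7 | 0.144 | 50.0 | 0.256 |
| 75% of affected subjects | 0.75 | 49.0 | 0.222 | 52.5 | 0.360 |
| 80% of affected subjects | 0.80 | 50.4 | 0.276 | 54.0 | 0.426 |
| All bilateral | 1.00 | 56.0 | 0.534 | 60.0 | 0.690 |

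An even chance of 32 malignant subjects needs 159 enrolled.

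**If 20% is a tube-level rate**

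Expected positive tubes at 140 are 280 × 0.20 = 56. With the 75% figure, the implied subject-level rate is 0.40/1.75 = 22.9% or 0.40/1.60 = 25%. P(at least 56 tubes) at 140 is then 0.51, and P(at least 32 subjects) by 150 is 0.70 to 0.87.

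**Power, for illustration only**

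The planning formula gives 80.7% at n = 32. I used an effective sample size of T²/(2 × n_bilateral × (1 + ρ) + n_unilateral), where T is the number of positive tubes and ρ is the correlation of *cytology* results between the positive tubes of one subject. For q = 0.60 to 0.75:

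- ρ = 0.75 gives 76–78% at 140 and 79–81% at 150.
- ρ = 0.5 gives 81–83% at 140 and 84–86% at 150.

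The plan does not give this ρ. Its 75% and 80% are argued from agreement in histology between tubes.

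**The case against.** The strongest defence is a design-effect reading. On that view 32 is a number of independent units, 56 tubes divided by 1.75 restores it, and 56 tubes are 28 bilateral subjects, which is 20% of 140. The chain closes and the planning formula returns its 80.7%. This explains where 140 came from, but it does not rescue the sentence. It needs every malignant subject to be bilateral, against the plan's own 75%. It makes 56 the mean, with a 53% chance of being reached. It also leaves a recruitment rule that counts 32 malignant *subjects*.

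Other points stand in part:

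- **The label may be the only slip.** If 20% is per tube, the enrolment step is arithmetically sound, though 56 is still only the mean at 140 (about 51%). The documents do not settle this, but they print the subject-level label three times.
- **Recruitment is target-driven, so 140 is only a projection.** This is true up to 150. The ten extra subjects may be an allowance for losses; their purpose is not stated. Even at 150 the expected count is 30.
- **True prevalence may exceed 20%.** It may, in women with a suspicious mass. Still, 20% is the figure that the plan chose and reasons from.
- **The rule on favorable discordance in Section 6.2 can add positive tubes.** Two tubes in each of 28 subjects is still at most 56 in expectation.

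A reader might infer that the trial is underpowered or needs more patients. The documents do not support that: the illustrative power runs from slightly below to slightly above the planned level, depending on a correlation that they do not give. Nor can the plan be faulted for the conversion formula, which is missing only from the extracted text. Counting the target in tubes instead of subjects would be a design preference, not the correction of an error.

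**Conclusion.** Wrong as written, in three places. With 20% taken as subject-level, the plan expects 28 malignant subjects at 140 and 30 at 150 against a requirement of 32. Expected positive tubes fall below 56 at both sizes on either reading of the 75% or 80% figure. The claim that 56 is likely therefore fails: the chance is about 9–28% at 140 and 18–43% at the cap.

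The tube figures rest on every malignant subject having an involved tube and on no sample losses. Both assumptions are favourable: the recruitment rule counts any malignancy, Section 5.2.4 limits the analysis to adequate samples, and Section 1.8 expects lower access and adequacy rates. If 20% is really a tube-level rate, the fault is mainly the label, and the subject target would probably be met by 150.

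Separately, Sections 6.4 and 6.5 give different correlations from the same evidence, and only 75% leads to 56.

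The consequence for sensitivity power is uncertain and may be small. Specificity is not at risk: about 140 × 0.80 = 112 negative subjects are expected against 18 required.

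**What to change.** In the synopsis and Sections 6.4 and 6.5:

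1. If 20% is a tube-level rate, correct the label. Otherwise restate the expected yield as 28 malignant subjects at 140 and 30 at 150, with about 45–50 and 48–54 positive tubes (at most 56 and 60 if all disease is bilateral). Say that these figures assume an involved tube in every malignant subject and are before sample losses.
2. Delete *statistically likely*.
3. Use one correlation value in both sections. If it is 80%, check the 56.
4. Have the sponsor recompute and restate sensitivity power at the expected yield by its own planning method, stating the assumed correlation of cytology results between positive tubes. The illustrative values above should not be adopted.

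A sentence on what is reported if the cap is reached before 32 malignant subjects would help but is optional.

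The cost is wording in three places and one power calculation, with no extra patients. The downside is that the stated figures become slightly less favourable.
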